3.0 INVESTIGATIONAL PLAN

3.1. Overall Study Design

This is a multiple-center, open-label, study of the PK, PD, and safety of a single dose of betrixaban at up to 80 mg in pediatric patients who meet study entry criteria. To adequately assess PD, any last dose of anticoagulant must not have been taken within one week prior to receiving betrixaban in this study.

Following an up to 30-day screening period, eligible patients who have provided Assent and whose parent or legal guardian has signed an Informed Consent will receive a single, oral dose of betrixaban at 40 mg or 80 mg. The screening visit may be an outpatient visit. Patients will enter (or if hospitalized, remain in) the hospital, clinical research unit, or Phase 1 unit on Day -1, the day before dosing with betrixaban is anticipated, and remain domiciled through 24 hours after betrixaban is administered. They may undergo the remainder of procedures as outpatients, including a Day 7 follow-up safety phone call.

Part 1 (the initial opening of the study) will be conducted in 21 adolescent patients (12 to < 18 years of age) who are assessed to be at risk for VTE but do not require immediate anticoagulation and whose coagulation parameters are normal. Each patient will receive a single, oral, hard gelatin capsule of betrixaban. The dose administered initially to adolescent patients will be 40 mg. After review of the safety data from patients who received 40 mg, additional adolescent patients may be dosed with 80 mg. There will be 2 cohorts of patients in Part 1 of the study. The cohorts are defined as follows:

- Cohort 1 will enroll 3 patients (at least one of each gender), each of whom will receive a single, oral dose of betrixaban at 40 mg in the fed state, and have 10 PK blood sampling time points.
- Cohort 2 will enroll 18 patients (6 patients in each of 3 PK sampling sequences), each of whom will receive a single, oral dose of betrixaban at 80 mg in the fed state, and undergo 5 PK sampling time points.

After dosing, patients will undergo serial blood sampling for PK-PD evaluations (the Schedule of Assessments detailing all procedures is provided in Table 5). The PK and PD data from Part 1 will be used for dose determination for the next youngest age group using POP PK and PBPK modeling and simulation. The primary PK parameters to be determined are $AUC_{(0-last)}$ and C_{max} . Other PK parameters to be determined are Total AUC $(AUC_{(0-\infty)})$, $t_{1/2}$, T_{max} , CL/F, and V_d/F . These will be estimated using POP PK methodology for age groups except the initial group of patients for which rich PK sampling is done.

Following analysis of Part 1 data and an amendment to the protocol, Part 2 of the study will commence and enroll 12 patients 2 to < 12 years of age. Each patient will receive an open-label, single oral dose of betrixaban; these patients must be able to take either the hard gelatin capsule or an oral, liquid formulation (once it has been developed and described in a future amendment to this protocol). Similar to Cohort 2, subjects will be assigned one of two PK sampling sequences based on data from Part 1. The cohort in Part 2 is defined as follows:

• Cohort 3 will enroll 12 patients (6 patients in each of 2 PK sampling sequences), each of whom will receive a single, oral dose of betrixaban in a fed state at a dose and route to be determined, based on the analysis of Part 1 data.

After dosing, patients will undergo serial blood sampling for PK-PD evaluations.

For all cohorts, safety assessments (evaluation of AEs, concomitant medications, routine chemistries [hematology, coagulation, serum chemistries]) will occur at protocol-specified time points.

The schema of the study is depicted in Figure 1. The Schedule of Assessments for the study is provided in Table 5.

Study Part	Part 1	Part 1	Part 2 - TBD Amendment
Cohort No.	Cohort 1	Cohort 2	Cohort 3
Age	12 to < 18 years	12 to < 18 years	2 to $<$ 12 years
Dose	40 mg	80 mg	TBD
n =	3 patients (one of each gender)	18 patients (at least two of each gender)	12 patients (at least two of each gender)
PK Sampling	Rich - 10 time points	Sparse - 5 time points	Sparse – TBD time points
PK Time Points	Pre-dose, 0.5, 1, 2, 3, 4, 6, 12, 24, 120 hours	Sequence A: pre-dose, 1, 3, 12, 120 hours Sequence B: pre-dose, 0.5, 2, 4, 24 hours Sequence C: pre-dose, 2, 3, 12, 24 hours	Sequence D: TBD Sequence E: TBD

Figure 1: Schema of Study 16-021

TBD = To be determined and later specified in a subsequent amendment to this protocol

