1.0 INTRODUCTION

Betrixaban is an oral anticoagulant that is a potent and specific inhibitor of human Factor Xa (FXa), an important validated target in the blood coagulation pathway. It binds to the active site of FXa to prevent thrombosis. As the maleate salt, betrixaban has a Molecular Weight (MW) of 567.98 and is available for oral administration as an Immediate Release (IR) capsule. It is rapidly absorbed with mean peak concentrations occurring 3 to 4 hours after oral administration. Oral bioavailability of an 80 mg dose is approximately 34%, and protein binding is approximately 60%. The drug exhibits nonlinear kinetics within the expected therapeutic dosing range with greater than proportional increases in plasma concentrations occurring with increased dose; maximum plasma concentration (C_{max}) and Area Under the Curve (AUC) at steady-state increased approximately 3-fold when the dose was doubled from 40 mg to 80 mg. Excretion is mostly unchanged through the bile with renal clearance approximately 17% of the absorbed dose. When administered after a high-fat, high-calorie breakfast, C_{max} and AUC were reduced by approximately 50% as compared to the fasting state.

Betrixaban is only weakly metabolized by major cytochrome P450 enzymes. It is a substrate for efflux proteins including permeability glycoprotein (P-glycoprotein or P-gp). When co-administered with the potent P-gp inhibitor ketoconazole, betrixaban concentrations were increased more than approximately 2-fold. Based on Population Pharmacokinetic (POP PK) analysis from the Phase 2 EXPLORE Xa study (Connolly et al., 2013) [1], a similar effect was observed when betrixaban was given concomitantly with amiodarone, another strong P-gp inhibitor. A drug interaction study with the P-gp substrate, digoxin, showed no significant interaction, and one with the strong inhibitor verapamil suggests that co-administration in fasted state increases both C_{max} and exposure to betrixaban.

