with severe renal deficiency was not needed and that dose adjustment should be limited to patients only on certain strong P-gp inhibitors when betrixaban was administered in the fed state, as was done in APEX. There is no evidence from any of the nonclinical or clinical PK studies conducted to date that suggests the mechanisms of Absorption, Distribution, Metabolism, and Excretion (ADME) of betrixaban will be different in the adolescent population. Therefore, POP PK simulations were used to predict the likely exposure response of a single 40 mg dose for the adolescent pediatric subset. Typical weights for adolescents (male and female) were obtained from the National Health and Nutrition Examination Survey (NHANES; USA). Males ranged from 40.7 to 67.3 kg and females from 41.8 to 56.2 kg. The range of body weight simulated overlaps with that of the patient population used in the adult POP PK models. The preliminary modeling studies suggested that for at least larger adolescents, the 80 mg dose would result in similar exposures to those observed in adults and that the relative exposure of a 40 mg dose in adolescent males is predicted to be approximately 60 to 88% of that of the male adult exposure receiving the 80 mg dose. Exposure in adolescent females is predicted to be 60 to 74% of that in adult females.

Portola Pharmaceuticals, Inc. plans to investigate betrixaban in a step-wise manner in pediatric subjects. The PK and PD parameters will be evaluated in the first study, starting with adolescents (12 to < 18 years of age) who can take a hard gelatin capsule and then proceeding to include progressively younger age groups (2 to < 12), as an oral pediatric formulation becomes available. For each age group, the PK and safety data will be analyzed and used to predict the weight-based dose to be used in the next younger age group in future studies. The doses predicted from Study 16-021 may then be used in the subsequent clinical efficacy and safety studies in pediatric patients.

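### The step from 40 mg to 80 mg requires only a safety review, although the protocol's own predictions imply above-adult exposure at 80 mg and Cohort 1 concentrations could be checked first

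*Protocol*

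**What the plan says.** The dose rationale in the protocol Introduction (1.0) reports preliminary population PK simulations. They suggest that "for at least larger adolescents, the 80 mg dose would result in similar exposures to those observed in adults". For the lower dose, the "relative exposure of a 40 mg dose in adolescent males is predicted to be approximately 60 to 88" percent of adult male exposure at 80 mg. For females: "Exposure in adolescent females is predicted to be 60 to 74% of that in adult females". The weights taken as typical were: "Males ranged from 40.7 to 67.3 kg and females from 41.8 to 56.2 kg". No simulated 80 mg figure is given for any weight. The same section describes the kinetics as nonlinear, with "greater than proportional increases in plasma concentrations occurring with increased dose", and reports roughly a 3-fold rise in adult steady-state Cmax and AUC between 40 and 80 mg.

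Section 3.1 gives 40 mg to 3 patients (Cohort 1, 10 sampling times each) and 80 mg to 18 (Cohort 2). The bridge between them is: "After review of the safety data from patients who received 40 mg, additional adolescent patients may be dosed with 80 mg". The Synopsis states the sequence without a condition. Sections 4.1 and 4.2 set no weight limit, Section 3.5 gives no dose adjustment, and Section 3.7 states that there is no DSMB.

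The stated uses of the PK data lie elsewhere. The Introduction says: "For each age group, the PK and safety data will be analyzed and used to predict the weight-based dose" for the next younger group. Section 3.1 says: "The PK and PD data from Part 1 will be used for dose determination for the next youngest age group". The Introduction adds that the adolescent data will confirm the models and show whether weight-based dosing is appropriate in adolescents, but does not place that before Cohort 2.

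**The concern.** Eighteen of the 21 planned Part 1 patients receive 80 mg. The only adolescent evidence available before that step is Cohort 1, which is richly sampled so that exposure can be seen. The rule asks for adverse-event and other safety findings from those 3 patients and does not ask for their concentrations. Three patients' safety findings at 40 mg say little about exposure at 80 mg. Their concentrations at least test the prediction on which the dose choice rests.

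The 40 mg predictions also appear to put 80 mg above adult exposure for some or all adolescents. The text supports adult-like exposure only for the larger ones and gives no figure for the rest.

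**Working it through.** **Inputs** (all from the protocol)
- Adolescent exposure at 40 mg relative to adults at 80 mg: males 0.60 to 0.88, females 0.60 to 0.74 (Introduction). The adult dose is explicit for males. For females it is read as 80 mg too.
- Fold rise from 40 to 80 mg, called k: above 2, because the rise is more than proportional. About 3 in adults at steady state (Introduction).
- Between-subject CV of AUC in adults: about 45% (Section 10.4).

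The 0.60 to 0.88 and 0.60 to 0.74 figures come from a model that is not in the documents. They cannot be reproduced and are taken as given.

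**Implied exposure at 80 mg relative to adults at 80 mg** = (ratio at 40 mg) × k. Adult 80 mg exposure is the reference on both sides, so no adult weight has to be assumed.
- k = 2 (lower bound), males: 2 × 0.60 = 1.20 to 2 × 0.88 = 1.76.
- k = 2, females: 2 × 0.60 = 1.20 to 2 × 0.74 = 1.48.
- k = 3 (upper sensitivity value only), males: 3 × 0.60 = 1.80 to 3 × 0.88 = 2.64.
- k = 3, females: 3 × 0.60 = 1.80 to 3 × 0.74 = 2.22.

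Conversely, equality with adults at 80 mg would need k = 1/0.60 = 1.67 at the low end and 1/0.88 = 1.14 at the high end. Both are below 2, so both would be less than proportional.

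**What 3 patients can show about the 40 mg prediction**
- SD of log exposure = √ln(1 + 0.45²) = 0.429. SE = 0.429/√3 = 0.248.
- The geometric mean is known within a factor exp(1.645 × 0.248) = 1.50 (90%, CV taken as known), or exp(2.920 × 0.248) = 2.06 (t on 2 df, at the same SD).
- Let R be true exposure divided by predicted exposure. The prediction is flagged as too low when the lower 90% limit of observed/predicted exceeds 1. With the CV known, the probability is Φ(ln R/0.248 − 1.645). With the SD estimated, it comes from the noncentral t on 2 df.
 - R = 1: 5% either way.
 - R = 1.25: 23% (CV known), 16% (SD estimated).
 - R = 1.5: 50%, 30%.
 - R = 2: 88%, 57%.
 - R = 3: above 99%, 86%.

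**The case against.** The strongest reply is that the check does not test the number that prompts it. The 1.20 to 1.76 range is what follows if the 40 mg prediction is right. In that case Cohort 1 would agree with the model 95% of the time and Cohort 2 would open as before. A 40 mg cohort also cannot measure the rise from 40 to 80 mg. This stands. The comparison guards against a wrong 40 mg prediction. The projection to 80 mg still relies on adult data, and its value is that someone must look at it by weight before dosing.

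The comparison with the next age group is also imperfect. Part 2 needs PK data because its dose is undetermined and its formulation may be new. The 80 mg dose was prespecified, was the standard adult dose, and the Introduction reports no evidence of different ADME in adolescents. That weakens the analogy but does not supply a reason to leave available concentrations unread.

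A reader might infer three stronger things that the documents do not support.
- *That the Introduction contradicts itself.* It claims similarity only for larger adolescents, at least. If the 0.60 end belongs to them, 1.20 can fairly be called similar. The mapping of ratios to weights is itself an inference, because the text does not give it.
- *That adolescents will have 1.80 to 2.64 times adult exposure.* The 3-fold rise is an adult steady-state figure and this is a single-dose study. A value of 1.80 at the low end would also sit badly with the statement of similarity. The documents do not say whether the simulations included the nonlinearity.
- *That 80 mg is unsafe.* The Introduction reports single doses up to 550 mg and 10-day regimens up to 120 mg every 12 hours as well tolerated in healthy subjects, and no QTc effect at 140 mg in adults. In proportional terms 1.76 × 80 mg is about 141 mg. Section 3.8.1 halts enrolment for major bleeding, a SUSAR or QTc prolongation.

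**Conclusion.** The point holds as a minor one. Taken at face value, the protocol's own figures put adolescent exposure at 80 mg at no less than 1.20 to 1.76 times adult exposure in males and 1.20 to 1.48 times in females. Section 3.1 nevertheless opens that dose to every eligible adolescent on safety review alone. Nothing forbids looking at the concentrations, but nothing requires it.

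The ranges rest on the approximate, preliminary 40 mg predictions, on reading the female reference as 80 mg, and on the more-than-proportional rise applying to a single dose in adolescents. The detection probabilities assume that the adult 45% CV carries over and treat the model prediction as exact. This is a gap in an escalation rule, not an arithmetic error, and it gives no grounds for a weight cutoff.

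**What to change.** In protocol Section 3.1, replace the escalation sentence with wording such as: *Dosing at 80 mg may begin once the safety data and the betrixaban plasma concentrations of the 3 Cohort 1 patients have been reviewed. The concentrations will be compared with the model's single-dose 40 mg prediction at each patient's weight, and exposure at 80 mg will be projected across the adolescent weight range.*

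The change belongs in the protocol only. SAP Section 3.1 repeats the sentence, but SAP Sections 1.0 and 6.11 say that Part 1 has been conducted. Adding the condition there would describe a review that the governing protocol did not require. For the same reason the change cannot act on patients already dosed; it is a comment on the rule as written.

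The cost is earlier assay of 3 × 10 = 30 samples that the protocol already collects and assays (Section 8.1), and a short pause before Cohort 2 against about 50 months of planned enrolment (Section 3.6). No extra blood is drawn and eligibility does not change. The check should be presented as coarse: it can show a roughly 2-fold miss in the 40 mg prediction but not a 1.25-fold one.

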7.0 STUDY CONDUCT

All procedures occurring during Part 1 of the study (administration of betrixaban in adolescents 12 to < 18 years of age) are detailed in Table 5, the Schedule of Assessments for Protocol 16-021. The patient will be domiciled in the hospital, clinical study site, or Phase 1 unit for Day 1 assessments, dosing, and through 24 hours post dose (i.e., start of Day 2). The 120-hour visit (i.e., Days 6) may be an outpatient visit. Part 1 of the study will enroll 21 adolescents 12 to < 18 years of age.

In Part 1 of the study, a total of approximately 53 to 63 mL of blood (depending on Cohort) will be drawn from each patient over a period of approximately 5 weeks. Approximately 2 mL will be drawn for each PK sample, 4.5 mL for each PD sample, and approximately 5 mL for hematology, chemistry, and coagulation samples, per local institution requirements.

This protocol will be amended prior to the commencement of Part 2 to specify age appropriate blood sampling volumes and time points.

To minimize pain and discomfort to pediatric patients during the blood sampling time points, sampling may occur via IV catheter or butterfly needle followed by saline flush. For patients with pre-existing central venous catheter or CVAD (i.e., central line, central venous line, or central venous access catheter) sampling may occur via these access points.

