7.4. Day 2: 24 Hours Post Dose

- Obtain vital signs (sitting) and body temperature (°C) (Section 9.1.3).
- Conduct limited PE, (Section 9.1.2); including weight.
- Draw blood for hematology, coagulation assessments (Section 9.1.6.1), and blood chemistry analysis (Section 9.1.6.2).
- Confirm PK-PD sampling requirement (Section 8.1, Section 8.2) based on subject-specific Cohort and Sequence Assignments. Refer to Table 5, Schedule of Assessments.
- Collect urine for urinalysis, include testing for blood in urine (Section 9.1.6.3).
- Record AEs.
- Record concomitant medications.
- Perform 12-lead ECG (Section 9.1.5).

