7.5. Day 6: 120 Hours Post Dose (Study Termination Visit)

- Obtain vital signs (sitting) and body temperature (°C) (Section 9.1.3).
- Conduct brief PE (Section 9.1.2); including weight.
- Draw blood for hematology, coagulation assessments (Section 9.1.6.1), and blood chemistry analysis (Section 9.1.6.2).
- Confirm PK-PD sampling requirement (Section 8.1, Section 8.2) based on subject-specific Cohort and Sequence Assignments. Refer to Table 5, Schedule of Assessments.
- Collect urine for urinalysis, include testing for blood in urine (Section 9.1.6.3).
- Record AEs.
- Record concomitant medications.
- Collect stool samples (if available) for occult blood testing (Section 9.1.6.4).

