8.0 PHARMACOLOGICAL ASSESSMENTS

8.1. Pharmacokinetic Assessments

The plasma portion of the blood samples will be assayed for determining the PK parameters of betrixaban. The following PK parameters will be calculated for each age groups using POP PK methodology as long as sufficient data is available:

- Terminal plasma half-life ($t_{\frac{1}{2}}$), determined by linear regression of the log concentration on the terminal portion of the plasma concentration–time curve. Half-life is calculated as $ln(2)/(-\beta)$, where β is the slope of the terminal portion of the log concentration–time curve.
- Time to maximum observed plasma concentration (T_{max}).
- Maximum observed plasma concentration (C_{max}).
- Area under the plasma concentration-time curve from 0 to last available measurable concentration (AUC_(0-last)) computed using the linear trapezoidal rule.
- Clearance (CL/F), calculated by dividing the administered dose by the AUC_(0-∞).
- Volume of Distribution (V_d/F) , calculated by dividing the dose administered by the plasma concentration at the first time point measured.
- Total area under the plasma concentration-time curve from time 0 to infinity (total AUC), computed as:
 - Total AUC $(AUC_{(0-\infty)}) = AUC_{(0-last)} + Cp_{last} / (-\beta)$ where $AUC_{(0-last)}$ is the area under the curve from time 0 to the time point of the last measurable concentration above the quantitation limit; Cp_{last} is the last measurable concentration above the quantitation limit; and β as defined above.

8.1.1. Blood Sample Collection

Blood samples for PK analysis will be collected using 3.2% Na Citrate as the anticoagulant. Blood samples for PK assessments will be collected 30 minutes prior to the dose administration, and at 0.5, 1, 2, 3, 4, 6, 12, 24, and 120 hours post dose with the 6 hour time point only being collected in the patients with rich PK sampling. Blood samples for patients in the POP PK analysis groups will be taken at time points based on the sequences to which each patient is assigned.

8.1.2. Urine Sample Collection

Urine samples will not be collected for centralized testing.

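### No 80 mg patient has more than one PK sample at or after 24 h, although safety blood is drawn from every patient at both 24 h and 120 h

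*Protocol*

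**What the plan says.** Protocol Section 3.1 puts "6 patients in each of 3 PK sampling sequences" in Cohort 2. Figure 1 sets the times: "Sequence A: pre-dose, 1, 3, 12, 120 hours Sequence B: pre-dose, 0.5, 2, 4, 24 hours Sequence C: pre-dose, 2, 3, 12, 24 hours". Table 5 shows the same times, although it labels the Sequence C rows as Cohort 3; Figure 1 is followed here.

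Safety blood does not depend on sequence. At 24 h (Section 7.4) every patient is to have this done: "Draw blood for hematology, coagulation assessments (Section 9.1.6.1), and blood chemistry analysis (Section 9.1.6.2". Section 7.5 repeats the instruction for the 120 h visit. PK sampling at those visits does depend on sequence: "Confirm PK-PD sampling requirement (Section 8.1, Section 8.2) based on subject-specific Cohort and Sequence Assignments".

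On volume, Section 7.0 gives "Approximately 2 mL will be drawn for each PK sample, 4.5 mL for each PD sample", then "approximately 5 mL for hematology, chemistry, and coagulation samples", and overall "a total of approximately 53 to 63 mL of blood (depending on Cohort) will be drawn from each patient".

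On estimation, Section 8.1 obtains the half-life from a terminal slope "determined by linear regression of the log concentration on the terminal portion of the plasma concentration". It sets no start time for the terminal phase and no minimum number of points. Section 3.1 assigns Cohort 2 to population PK by age group. Section 2.3 instead speaks of parameters for each patient. SAP 6.5.1 treats the sparsely sampled patients as an average, and SAP 6.5.2 runs no analysis of half-life, AUC(0-inf), CL/F or Vd/F.

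**The concern.** The Summary of Key Changes (Amendment 2) explains the cut to five PK times as sparing children pain and discomfort. Leaving out a PK tube at a visit where blood is drawn anyway spares no puncture. It does cost information where the design is thinnest.

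Half-life and AUC(0-inf) depend directly on the terminal slope, and CL/F depends on it through AUC(0-inf). Section 3.1 lists all three and intends Part 1 PK to set the dose for the next age group. Cohort 1 cannot fill the gap. It has three patients at 40 mg, and Section 1.0 describes nonlinear kinetics, with steady-state exposure rising about 3-fold when the dose is doubled from 40 to 80 mg. The 80 mg tail therefore has to come from Cohort 2.

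**Working it through.** **1. Reproduce the stated blood volume.** Inputs: 2 mL per PK tube, 4.5 mL per PD tube and 5 mL per safety draw (Section 7.0). Table 5 gives four safety draws (screening, Day -1, 24 h, 120 h) and five PD samples per patient.
- Cohort 1: 10×2 + 5×4.5 + 4×5 = 62.5 mL.
- Cohort 2: 5×2 + 5×4.5 + 4×5 = 52.5 mL.

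These round to the stated 63 and 53 mL. Pregnancy-test blood is assumed not to be counted.

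**2. Count the late PK samples in Cohort 2.**

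| Sequence (n) | PK after 4 h | PK at or after 24 h | Safety blood |
|---|---|---|---|
| A (6) | 12, 120 h | 120 h | 24 and 120 h |
| B (6) | 24 h | 24 h | 24 and 120 h |
| C (6) | 12, 24 h | 24 h | 24 and 120 h |

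No patient (0 of 18) has PK at both 24 h and 120 h. There are 12 samples at 24 h and 6 at 120 h, from different children. In A and C (12 of 18) a line from 12 h has two points and no residual degrees of freedom. B has one point.

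**3. What the two-point lines would give.** Illustrative curve: C(t) = R·exp(-at) + exp(-bt), with an assumed fast half-life of 3–6 h, R of 3–5 and a terminal half-life of 20–37 h. The 12–24 h line (C) returns about 10–16 h and the 12–120 h line (A) about 18–32 h. For example, with fast half-life 4 h, terminal 20 h and R = 3, C gives 10.9 h, A gives 17.9 h, and a 24–120 h pair would give 19.4 h.

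**4. Precision of ln(C24/C120).** Between-subject CV is 45% (Section 10.4, for AUC(0-last)), so the log-SD is sqrt(ln(1+0.45²)) = 0.429. Residual CV is assumed to be 15–30%, a log-SD of 0.149–0.294.
- Comparing raw group means only: sqrt(0.429²+0.149²)×sqrt(1/12+1/6) = 0.227 at 15%, and 0.260 at 30%.
- Current design, linking each child's own samples (random intercept per child, free mean at each time, generalised least squares): 0.099 at 15%, 0.185 at 30%.
- With the added tube: residual SD × sqrt(2/18) = 0.050 at 15%, 0.098 at 30%.

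The like-for-like ratios are 0.099/0.050 = 1.98 and 0.185/0.098 = 1.89.

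**5. Convert to slope CV.** CV = SE/(96k), with k = ln 2/half-life. At 60 h, 96k = 1.109, so at 15% residual error the CV goes from 8.9% to 4.5%. Adding an assumed 20% between-child CV in the slope itself, and covering half-lives of 20–60 h and residual error of 15–30%, the same model gives 9.9–19.3% now and 4.9–10.0% with the tube. The ratio stays near 2.

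**6. Mean 120 h concentration.** Going from 6 to 18 samples divides the standard error by about sqrt(3) = 1.73, so a CV of about 22–41% becomes about 13–23%. The lower end is 45% between-subject and 30% residual CV with a common slope: sqrt(exp(0.429²+0.294²)-1) = 56% per child; 56/sqrt(6) = 23% and 56/sqrt(18) = 13%. The upper end needs a per-child CV near 100%, which arises when slopes also differ. More variable elimination would raise both figures but not change the ratio.

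**7. Volume after the change.** 52.5 + 2 = 54.5 mL. Adding a PD tube as well would give 59.0 mL.

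**The case against.** A reader might infer that no 80 mg patient yields a terminal slope at all. The documents do not support that. Section 8.1 fixes neither when the terminal phase starts nor how many points are needed, and Section 1.0 puts the adult peak at 3 to 4 h. Two-point lines from 12 h are therefore possible in A and C, though step 3 suggests they would run short.

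A reader might also infer that the 24–120 h decline has to be read by comparing different children, with a gain of 3-fold or more from pairing. That ignores the planned population PK, which under Section 10.5 uses every sample from every patient. Sequence A links 12 to 120 h within child, and C links 12 to 24 h. Once this is used, the gain is about 2-fold.

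Three further points stand in part.
- The primary parameters hardly benefit. On the same kind of assumptions the CV of the average-profile AUC(0-last) moves only from about 11% to 10.5%, and late tubes say nothing about Cmax. Half-life is conditional on adequate data in the protocol, and the SAP does not analyse it. But the SAP's reason is that development ended, not that the sampling was adequate.
- Missed Day 6 visits are not wholly unprotected. Section 3.4 replaces only undosed subjects, but Section 10.7.1 allows replacements so that enough patients are evaluable for the primary PK parameters. That is permitted, not required.
- The SAP reports that Part 1 has been performed and Part 2 will not be, so an amendment can no longer add these samples to completed patients.

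**Conclusion.** The point holds as a sampling-efficiency weakness, mainly for secondary parameters. At 80 mg each child contributes exactly one PK sample at or after 24 h, and six samples carry the 120 h tail, while blood is drawn from all 18 children at both times. Population PK recovers part of the loss. One more tube would still roughly halve the standard error of the 24–120 h slope and reduce the CV of the mean 120 h concentration by a factor of about 1.7. Half-life and AUC(0-inf) benefit, CL/F slightly.

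The counts and volumes come directly from the protocol. The precision figures rest on assumptions: 45% CV applied to concentrations, 15–30% residual error, a 20–60 h half-life, 20% spread in slope for the 10–20% range, and 120 h values above the quantitation limit. The documents give neither a half-life nor a quantitation limit. The random-intercept calculation approximates a full population PK model.

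**What to change.** In Table 5 and Figure 1, add a 2 mL PK tube at 24 h for Sequence A and at 120 h for Sequences B and C, taken at the same puncture as the scheduled safety blood. All 18 patients then have both times. The range in Sections 7.0 and 9.1.6 is cohort-specific, so its lower figure should change from 53 to about 55 mL. Correct the Sequence C label in Table 5 at the same time.

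The cost is one tube and one assay per Cohort 2 patient, with no added visit or venepuncture, plus a small amendment. Where Part 1 sampling is already complete, the remaining step is in reporting: give the number of patients behind the 24 h and 120 h points of the 80 mg average profile, and say that its last segment rests on at most six planned samples. Carry the change into any later study that reuses these sequences.
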